## **STATEMENT OF COMPLIANCE**

The study will be conducted in accordance with the International Conference on Harmonisation guidelines for Good Clinical Practice (ICH E6), the Code of Federal Regulations on the Protection of Human Subjects (45 CFR Part 46), and the NIDCR Clinical Terms of Award. All personnel involved in the conduct of this study have completed human subjects' protection training.

## PROTOCOL SUMMARY

- Title:** Tailored Self-Management of TMD Pain using Health Information Technology
- Short Title** TMD Self-Care Study
- Précis:** This protocol describes activities to determine the feasibility and acceptability of proposed methods for a subsequent clinical trial of a tailored self-management program (PACT) designed to decrease pain in participants with temporomandibular disorders (TMD). The PACT program is a personalized program of exercise and behavioral changes implemented through a web-based program supported by a health coach. For this feasibility and acceptability study, 80 adults with TMD pain will be randomized either to the PACT program or to traditional self-care. This sample size was determined as the number needed to evaluate feasibility and acceptability of the primary intervention and determine the utility of the outcomes measures that will be collected at baseline, 8-week and 16-week follow-ups.
- Objectives:**
- Objective 1:** To evaluate the feasibility and acceptability of methods to conduct a full-scale multi-site randomized clinical trial comparing PACT self-management with traditional self-care for TMD. Methods to be tested are:
- a. Participant recruitment, consent, enrollment, and retention;
  - b. Participant adherence to the study;
  - c. Completion of study questionnaires at 8-week and 16-week follow-up;
  - d. Participant perceptions of the online website functionality and acceptability;
  - e. Participant perception of health coaches in the PACT program.
- Objective 2:** To demonstrate ability to accurately capture outcome measures to be used in the multi-site study.
- Objective 3:** To demonstrate ability to accurately capture potential mediators/moderators of specific behavioral and psychosocial factors on the PACT program's observed effects on pain and functioning outcomes through self-report. Hypothesized mediators are self-efficacy, participant activation exercise frequency and sleep quality. Hypothesized

moderators are disability status, catastrophizing, depression, repetitive strain from oral habits, perceived stress, and social support.

**Population:** The study will recruit 80 adults with TMD pain more than once a week from the HealthPartners Dental Group and selected dental clinics within the HealthPartners research network will be randomized. Ten participants will provide feedback on the online program during the development phase.

**Phase:** Pilot

**Number of Sites:** 1 – HealthPartners Institute (HPI)

[figure not shown]
**Description of Intervention:** Personalized Activated Care and Training (PACT) is a personalized 8-week progressive program with a health coach to enhance understanding, compliance, and success in self-management of TMD pain.

**Study Duration:** 12-18 months

**Subject Participation Duration:** 4 months

**Estimated Time to Complete Enrollment:** 8 months

## 2 INTRODUCTION: BACKGROUND INFORMATION AND SCIENTIFIC RATIONALE

### 2.1 Background Information

**Health problem.** Temporomandibular disorders (TMD) are the second most common musculoskeletal pain condition, affecting about 10% of the general population. In 2011, the Institute of Medicine (IOM) made research on pain conditions such as temporomandibular disorders (TMD), among the highest priorities because of its high prevalence, functional limitations, missed work, opioid dependency, and high health care cost. More than 100 million U.S. adults are affected by chronic pain conditions, costing between \$560 and \$635 billion annually in medical care and lost productivity. TMDs are the second most common musculoskeletal pain condition, affecting about 10% of the general population.

**Interventions.** Self-management programs provide a convenient mechanism for health care professionals to improve the management of pain conditions at an earlier point in their development, when it is easier to prevent chronic pain. The study will employ a self-management program, entitled Personalized Activated Care and Training (PACT) that is a tailored 8-week progressive web-based training program supported by a health coach to enhance understanding, compliance, and success in improving TMD pain. The program provides 8 weeks of structured didactic and experiential training on exercises and cognitive-behavioral training to reduce risk factors that contribute to delayed recovery and enhance protective factors that have evidence of improving TMD pain.

**Relevant research and scientific justification.** Chronic pain in the jaw, head, and face are caused by conditions such as joint disk disorders, myofascial pain, and osteoarthritis. These conditions may begin with an injury or strain, but often persist due to the presence of risk factors such as repetitive strain, depression, poor sleep, stress, maladaptive postures, depression, catastrophizing, and others factors that can delay recovery, increase peripheral and central sensitization, and, ultimately cause the persistence of chronic pain. When an acute TMD pain becomes chronic it often results in severe jaw pain, headaches, missed work, disability, opioid dependency and higher cost of care. Half of the persons seeking care for TMD still have pain 5 years later, and 15% to 20% of them have long-term disability. The care for these patients often escalates to high-cost and higher-risk passive interventions such as opioid analgesics, polypharmacy, high-tech imaging, and surgery. Yet, clinical trials and systematic reviews have not found the outcomes of passive therapies to be any better than self-management strategies that activate the patient through exercise and cognitive and behavioral changes. The Institute of Medicine states the clinicians' primary role in caring for chronic pain requires guiding, coaching, and assisting patients with day-to-day self-management in addition to evidence-based medical treatments. However, most health professionals lack the time and training to perform this role, and find little support and reimbursement for doing so. As the Institute of Medicine simply stated, we need a revolution in health care to replace our current passive model of *doctor-centered* care with patient-centered care that integrates robust self-management with evidence-based treatments. Clinical trials have found that patients who are engaged in self-management have significantly more successful outcomes than passive biomedical treatments alone. Thus, the use of on-line self-management programs provides a convenient and cost-effective mechanism for health professionals to improve the management of pain conditions at an earlier point in their development, when it is easier to prevent chronic pain. While training patient in self-management is a laudable goal, the implementation as part of routine care is a challenge that

most health professionals do not embrace due to time and training, and reimbursement. The use of Consumer Health Information Technology (CHIT) to empower and engage consumers to better manage their health is becoming an acceptable alternative to in-person training session for self-management. The use of CHIT has distinct advantages of being flexible, personalized, scalable, clinically effective, and cost-effective, and can help transform the health care system by allow most health professional to use with patients. The Center for Information Technology Leadership (2008), a nonprofit research center, concluded that CHIT could save \$19 billion annually by focusing on prevention, early intervention, self-management, and evidence-based care using CHIT. Partner's Center for Connected Health also concluded that health care will not be reformed without consumer engagement. However, these goals will not become reality unless research such as this study demonstrates efficacy. This project uses CHIT to engage patients, enhance understanding, adherence, and document outcomes.

## 2.2 Rationale

While several distinct pathophysiological mechanisms may occur in TMD pain conditions, it is important to understand and address the complex interaction of diverse factors that can initiate, perpetuate, delay recovery, or even protect patients from increasing severity of pain due to changes to peripheral and central sensitization. Maixner, et al (2011) have identified biopsychosocial and genetic risk factors that contribute to the onset and persistence of painful TMD in the OPPERA Study. Their conceptual model describes the changes that can occur in human biology, behaviors, and relationships when a person develops a chronic pain condition. This model suggests the need to address the "whole" patient by addressing multiple inter-related risk factors that play a role in the progression of the pain and can be influenced to prevent progression. Addressing these factors can lead to tailored treatment strategies with more predictable outcomes in reducing pain, peripheral, and central pain sensitization by influencing the underlying causes. *Risk factors* such as behavioral factors (e.g., repetitive strain, muscle tension, postural habits), emotional risk factors (e.g., anxiety, depression), comorbid conditions (e.g., fibromyalgia), and cognitive factors (e.g., poor understanding of etiology, unrealistic expectations, somatization, coping strategies, catastrophizing) have been found to be important in the progression to chronic persistent pain. For example, our studies found depression, somatization, fibromyalgia, and premorbid perceived stress to be significant risk factors that increase central sensitization and play a key role in predicting poor outcomes in TMD pain patients. By reducing these factors, they will encourage healing and lessen pain. On the other hand, *protective factors* can reduce delayed recovery and also improve normal healing, and prevent chronic pain. Factors such as level of coping, self-efficacy, patient beliefs (e.g., perceived control over pain), and social support can lead to more positive outcomes. Each of these factors are integrated into the PACT program.

The PACT program provides structured education, exercises, and cognitive-behavioral training that have evidence of improving TMD pain by changing these risk factors and enhancing protective factors. The program is based on clinical guidelines, clinical experience, clinical trial research, research on risk factors, protective factors, and systematic reviews of self-management efficacy of pain. The educational content is based on an existing on-line training course on preventing chronic pain and has been adapted for the PACT program.

## **2.3 Potential Risks and Benefits**

### **2.3.1 Potential Risks**

Potential risks include:

- 1) Although the program includes simple exercises and behavioral changes, participant conditions may not improve or may have their pain aggravated. This is minimized by providing personalized experiential instruction on the exercises and behavioral changes and cautioning participants to seek additional care if their condition does not improve or worsens. Participants will be screened by TMD diagnostic criteria to ensure their condition is appropriate for the study.
- 2) There is some risk associated with the release of personal health information (PHI) from health records. The investigators will protect subjects' records so their name, address, phone number, and clinical information is kept private and will not be released without participants' specific written permission. All data will be stored in a de-identified format without reference to participant identity.

### **2.3.2 Potential Benefits**

Potential benefits include:

- 1) While this study is not designed to test the efficacy of the PACT program, participants may derive benefit from participation in the study with a reduction of pain, improvement in daily activities, and engagement in self-management strategies. In addition, the improved knowledge from use of PACT will enhance the participants' own understanding of their condition and how to self-manage it. The information and knowledge gained from the study may be valuable in improving care and management of TMD pain and implementation of evidence-based care with providers.
- 2) The importance of knowledge gained. This research may provide information for the development of new, more effective strategies to predict, prevent, and manage TMD pain in participants of all racial and ethnic groups, as well as improve understanding and development of efficacious, cost-effective treatments that contribute to better outcomes for participants.

### 3 OBJECTIVES AND OUTCOME MEASURES

#### 3.1 Study Objectives

##### 3.1.1 Objective 1

**Objective 1** is to evaluate the feasibility and acceptability of methods to conduct a full-scale multi-site randomized clinical trial comparing PACT self-management with traditional self-care for TMD.

- Participants will find the PACT program acceptable as an intervention to help improve TMD pain and the study will successfully recruit participants to test the intervention.
- The study will reach recruitment, randomization, and retention goals
- The study will satisfactory collect study data (screening, baseline, follow up, qualitative) for evaluation purposes

Methods to be tested are:

- a. Participant recruitment, consent, enrollment, and retention;
- b. Participant adherence to the study;
- c. Completion of study questionnaires at 8-week and 16-week follow-up;
- d. Participant perceptions of the online website functionality and acceptability;
- e. Participant perception of health coaches in the PACT program.

##### 3.1.2 Objective 2

**Objective 2** is to demonstrate ability to accurately capture outcome measures to be used in the multi-site study.

- The PACT study will accurately define and capture accurate primary and secondary outcomes measures (jaw functioning, pain severity and pain interference) to be used in a larger multisite study

##### 3.1.3 Objective 3

**Objective 3** is to demonstrate ability to accurately capture potential mediators/moderators of specific behavioral and psychosocial factors on the PACT program's observed effects on pain and functioning outcomes through self-report. Hypothesized mediators are self-efficacy, participant activation exercise frequency and sleep quality. Hypothesized moderators are disability status, catastrophizing, depression, repetitive strain from oral habits, perceived stress, and social support.

- The PACT study will accurately define and capture hypothesized mediators including self-efficacy, participant activation exercise frequency and sleep quality
- The PACT study will accurately define and capture hypothesized moderators including disability status, catastrophizing, depression, repetitive strain from oral habits, perceived stress, and social support.

### 3.2 Study Outcome Measures

#### 3.2.1 Objective 1 Outcome Measures

Four study methods will be tested, each with specific measures to evaluate feasibility and acceptability. The methods to be tested and their associated measures are as follows:

- a. Participant recruitment, consent, enrollment, and retention: Feasibility of participant recruitment will be measured by demonstrating the ability to meet the enrollment target for the study (N=80). Milestones toward meeting target enrollment are: the ability to identify an adequate number of individuals that meet eligibility criteria, and number (%) of individuals consenting to participate compared with the total number contacted.

Objective	Constructs	Target outcomes
Recruitment (identify)	
 
1. Identification of TMD patients using HPDG electronic records (EHRs)
 
2. Percentage of participants recruited by both electronic health records (EHR) and self-referral
 
	
 
1. Generate a list of new TMD patients for possible enrollment in the study during the 6 months of recruitment
 
2. Participants will be recruited from both the search of the EHR and self-referral using brochures in the clinics
 

Recruitment (enroll and consent)	
 
1. Percentage of contacting participants who meet eligibility criteria
 
2. Percentage of contacted participants who consent to enroll in study
 
	
 
1. 80% of participants who talk with staff meet eligibility criteria for study
 
2. 30% of eligible participants contacted enroll in the study
 

Recruitment (retention)	
 
1. Percentage of participants who start program after randomization
 
	
 
1. 95% participants recruited for each arm start program after randomization
 

- b. Participant adherence will be measured by accessing the website at each of the follow-up periods. Participant adherence to the study will also be measured by number of participants completing all 8 on-line modules (with a goal of 80%).

Objective	Constructs	Target outcomes
Intervention (adherence/compliance)	
 
1. Number of participants accessing all online lessons
 
2. Use of health coaches (PACT arm)
 
3. Pain and risk assessment instruments within the PACT program (PACT arm)
 
4. Time spent in online program per week (PACT arm)
 
	
 
1. 80% of enrolled participants access all lessons as measured by Web site hits
 
2. 90% of participants in PACT have at least 3 phone meetings with the health coach (PACT arm)
 
3. Completion of all pain and risk assessment instruments within the PACT program (PACT arm)
 
4. Time spent in each module of online program per week (PACT arm)
 

- c. Completion of questionnaires at 8-week and 16-week follow-ups, and program evaluation. Completion of questionnaires will be measured by the percent of participants who complete the 8-week and 16-week follow-up questionnaires and, the program evaluation. We expect that at least 80% of participants will complete all questionnaires.

Objective	Constructs	Target outcomes
Evaluation (adherence/compliance)	
 
1. Number of participants completing 8-week and 16-week follow-up questionnaires
 
2. Number of participants completing the program evaluation survey questions (PACT arm)
 
	
 
1. 80% complete both 8- and 16-week follow-up questionnaires
 
2. 80% of participants in PACT group complete the program evaluation form
 

Evaluation (instrument performance)	
 
1. Responsiveness to constructs in subscales of the survey.
 
2. Inter-correlations between scales
 
3. Participant burden is measured by time to complete.
 
	
 
1. Outcome variables show changes in the expected direction
 
2. Outcome variables are associated with mediator/moderator factors in the expected direction
 
3. 90% of participants complete all surveys in estimated time
 

- d. Participant perceptions of the online website functionality and acceptability will be measured by participant reports of problems and ease of use reported at the program

evaluation. These reports will come from the number of phone calls/questions received about web-site issues, and from the qualitative interview.

Objective	Constructs	Target outcomes for both arms
Web-Site functionality	
 
1. Heuristic evaluation of functionality of the Web-based platform
 
2. Mode of administration acceptance
 
	
 
1. Less than 10% of participants note problems with website via comments section in each module or during program evaluation
 
2. 90% of participants rate web-site accessibility for learning the concepts as very good to excellent
 

Intervention (acceptability)	
 
1. Identification of self-reported barriers for improvement
 
2. Pace in which participants complete the program
 
	
 
1. 80% of participants identify at least one self-report barrier for improvement
 
2. 60% of participants follow the timeline on the Web site to complete in 8 weeks
 

Participant perceptions of program	
 
1. Qualitative interviews of participants
 
	
 
1. At least ten randomly selected participants will agree to be interviewed to provide their perceptions about the content of the program and at least 90% report that it is acceptable.
 

- e. Participant perception of health coaches in the PACT program will be evaluated by qualitative interviews of both health coaches and participants

Objective	Constructs	Target outcomes for both arms
Participant perceptions of health coach	
 
1. Qualitative interviews of participants about health coaches
 
	
 
1. At least ten randomly selected participants will agree to be interviewed to provide their perceptions about the content of the program. Of at least 10 participants interviewed, 90% will report that they found the health coaches to be helpful.
 

---

Health coach perception of program	1. Qualitative interviews of participants	1. Health coaches will provide their perceptions on the program and areas for development
------------------------------------	---	---

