## **5 STUDY ENROLLMENT AND WITHDRAWAL**

### **5.1 Subject Inclusion Criteria**

In order to be eligible to participate in this study, an individual must meet all of the following criteria:

- Age 18 or older
- Able and willing to access the internet on a regular basis
- Able and willing to participate in weekly phone coaching calls
- Able to read and speak English\*\*
- Willing and able to comply with all study procedures and be available for the duration of the study:
- Has a diagnosis of TMD pain using a self-report screener, specifically:
  1. Reporting pain in the jaw or temple area (on either side) in the last 30 days.
  2. Reporting pain or stiffness in the jaw on awakening in the last 30 days.
  3. Reporting changes in pain (either better or worse) in the jaw or temple area (on either side) in the last 30 days, after the following activities: chewing hard or tough food, opening the mouth or moving the jaw forward or to the side, jaw habits such as holding teeth together, clenching/grinding, or chewing gum, or other jaw activities such as talking, kissing, or yawning
- Has a frequency of TMD pain more than once a week with pain in the past 6 months
- Provides an electronically signed and dated informed consent form.

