Tailored Self-Management of TMD Pain using Health Information Technology

NIDCR Protocol Number: 16-054-E

NIDCR Grant Number: U01 DE025609

Principal Investigator: [name], MS

March 20, 2017

Final Analysis Plan

We will perform the following analysis and present results in preparation of the full study. The Primary outcomes for this study are acceptability and feasibility of the methods. The study is not sufficiently powered to test for mean changes from baseline to follow-up. Thus, we will conduct the following descriptive analysis at noted in the outcome measures:

- Number of participants, baseline characteristics and outcomes at baseline will be summarized descriptively
- Summary measures will include mean values (standard deviation SD) for continuous variables and frequency distribution for categorical variables.
- Outcome measures will be analyzed for departure of normality, and standard transformations will be applied.
- Percent of participants completing the measures for outcomes, mediating and moderating factors at baseline and each follow-up periods

The acceptability of the outcomes, mediating and moderating measures at baseline and followup periods

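### Two of the three instrument-performance targets ask only for the right sign, so improvement would pass as responsiveness without being evidence of it

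*Protocol*

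**What the plan says.** The instrument-performance row of Protocol 3.2.1(c) pairs three constructs with three targets.

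- Construct 1, "Responsiveness to constructs in subscales of the survey", is met if "Outcome variables show changes in the expected direction".
- Construct 2, "Inter-correlations between scales", is met if "Outcome variables are associated with mediator/moderator factors in the expected direction".
- Construct 3, participant burden, has a number: "90% of participants complete all surveys in estimated time".

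For the first two there is no magnitude, interval, comparator, arm, time point or count of scales that must comply. The row does not say whether change is within arm, pooled or between arms.

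Entry depends on symptoms. Protocol 5.1 requires, among other things, "Reporting pain in the jaw or temple area (on either side) in the last 30 days" and pain more than once a week. The telephone screen (Appendix E) needs at least 2 points. Protocol 5.11 lets participants use medication, splints and physical therapy alongside the study program.

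Protocol 11.4 and the SAP have the same analysis list. Both are descriptive and state that "The study is not sufficiently powered to test for mean changes from baseline to follow-up". They cover baseline summaries, means with SDs, frequencies, normality checks and completion percentages. No change score, correlation or interaction appears.

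**The concern.** Responsiveness is a scale's ability to register real change when it occurs. A mean that has moved the right way does not show this, because such a move also arises from chance, from regression to the mean after enrolment on recent symptoms, from natural recovery and from concomitant treatment. As written, target 1 cannot separate these from a responsive instrument. This is a stated pass rule that gives the wrong signal, which is more serious than a missing detail.

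Target 2 has the same sign-only form and no stated strength, so a negligible correlation satisfies it. It also puts mediators and moderators together without saying what the correlation is meant to show.

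Protocol 11.2 says the pilot, together with previous findings, will inform the larger trial. A report that the scales proved responsive would carry weight there, on little evidence.

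**Working it through.** **No plan figure to reproduce.** Targets 1 and 2 have no number attached, and the sample size of 80 rests on feasibility and resources, not on a formula. The calculations below are illustrative.

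**Inputs from the documents.** There are 80 participants randomised 1:1. The 80% target for completing both follow-ups gives 0.80 × 80 = 64 completers, or 32 per arm.

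**Assumed inputs (not in the documents).** Scores are normal with SD 1 and there is no true change. A fraction s of the source population qualifies: 0.9 or 0.8 (loose entry) or 0.5 (tight entry). Correlations between occasions are as given below.

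**Step 1: chance alone.** With no selection, the mean change is symmetric about zero and has the right sign 50% of the time. Two primary outcomes both have it 25% of the time if their changes are uncorrelated, and 37% if they correlate at 0.7.

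**Step 2: regression to the mean, pooled or within arm.** Taking the top fraction s of a normal distribution shifts its mean by k = φ(z)/s, where z is the cut-off. So k = 0.195, 0.350 and 0.798 for s = 0.9, 0.8 and 0.5.

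*Model A, selection at the screener, before baseline.* P(pass) = Φ[(a − b)·k / √(2(1 − b)/n)]. Here a is the screen-baseline correlation (0.80 to 0.90), and b is both the screen-follow-up and the baseline-follow-up correlation (0.55 to 0.70).
- Lowest corner, s = 0.9, a = 0.80, b = 0.70, n = 64: 0.10 × 0.195 / √(0.6/64) = 0.0195/0.0968 = 0.20, and Φ = 58%.
- Highest corner for s = 0.8, a = 0.90, b = 0.55: 0.35 × 0.350 / √(0.9/64) = 0.1225/0.1186 = 1.03, and Φ = 85%.

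*Model B, selection on the baseline score itself, baseline-follow-up correlation r from 0.5 to 0.9.* The expected fall is (1 − r)k, the SD of change is √((1 − r)²v + 1 − r²) with v = 1 + zk − k², and P(pass) = Φ(√n × fall/SD).
- Example, s = 0.8, r = 0.7: fall 0.30 × 0.350 = 0.105, SD 0.75, ratio 0.14, and Φ(8 × 0.14) = 87%.

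| s | Model A, n = 64 | Model B, n = 64 | Model B, one arm, n = 32 |
|---|---|---|---|
| 0.9 | 58–72% | 64–79% | 60–72% |
| 0.8 | 64–85% | 74–93% | 67–85% |
| 0.5 | 80–99% | 93% to over 99% | 85–99% |

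For one arm under Model A, the lowest corner is Φ(0.0195/√(0.6/32)) = Φ(0.14) = 56%.

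**Step 3: between arms.** Randomisation makes regression to the mean cancel on average, so the null pass rate returns to 50%.

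**Step 4: would an interval on within-arm or pooled change be enough?** No. Under Model B with n = 64, the lower 95% limit still exceeds zero with no true change in 15% of samples (s = 0.8, r = 0.8) to 86% (s = 0.5, r = 0.6). Only the between-arm contrast removes the artefact. Its 95% half-width is 1.96 × √(2/32) = 0.49 SD of change. For comparison, the standardised response mean in one arm has a half-width near 1.96/√32 = 0.35.

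**Step 5: what a target 2 correlation can show.** In 20,000 simulated trials of 64 participants, a purely prognostic factor (slope 0.3 SD, no interaction) had the right sign 99% of the time. A pure moderator (interaction of 0.5 or 1.0 SD, no average association) had it 50% of the time, the same as noise. The correlation says how scales relate and nothing about moderation. Its half-width near zero is about 1.96/√61 = 0.25.

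**The case against.** **The entry rule is loose, so regression to the mean may be modest.** This stands. The screener does not score pain intensity: brief pain plus stiffness on waking reaches 2 points. Jaw function, a primary outcome, plays no part in selection. Baseline is measured after screening, which weakens the effect, although overlapping 30-day recall limits that. A reader might infer that regression to the mean makes a pass almost certain. That needs tight selection, which the documents do not support. With 80–90% of the source population qualifying, Model A gives 58–85%, and read between arms the figure is 50%.

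**Correlation is a proper tool for target 2.** This also stands. The construct concerns relations between scales and sits under instrument performance. "Hypothesized moderators are disability status, catastrophizing, depression, repetitive strain from oral habits, perceived stress, and social support" might lead a reader to treat target 2 as a mistaken test of moderation. The documents do not present it so: Objective 3 asks only for the ability to capture these factors, and no moderation analysis is planned.

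**These targets may decide nothing.** A reader might infer that they determine which scales enter the multisite trial. No passage gives a keep-or-drop rule. What remains is a responsiveness conclusion without support.

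**Being unpowered to test change does not prevent describing it.** True, and the SAP does promise means and SDs. But visit-by-visit means and SDs do not give the SD of change or an interval for it, because those need the within-person correlation. The SAP's general pointer to the outcome measures adds no analysis of change or correlation.

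**Conclusion.** The point holds for targets 1 and 2 of the row, and not for target 3, which is numeric. Both are sign-only and have no planned analysis behind them. Under target 1, a scale with no true change passes about 50% of the time by chance. If change is read within arm or pooled, it passes more often: about 58% to over 99% with 64 pooled completers, and slightly lower in a single arm. That range depends entirely on assumed selection, correlations and normality. The direction is secure and the size is not. Concomitant treatment and natural recovery could raise the pass rate further and are not modelled. Movement in the expected direction is therefore not evidence of responsiveness. Target 2 is legitimate as a description of how the scales relate, but it needs an estimate with an interval and a statement of what it does not show. A change is worth making, though it affects no stated go/no-go decision.

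**What to change.** **Target 1 (Protocol 3.2.1(c), 11.4 and SAP).** Replace the sign rule with the following, for each outcome at weeks 8 and 16:
- mean change and standardised response mean by arm, each with a 95% CI;
- the between-arm difference in change with a 95% CI.

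Report these descriptively, with no pass threshold. State that within-arm change includes regression to the mean and other treatment. State also that a between-arm difference near zero may reflect the program and not the scale, since the half-width is about 0.49 SD and power for a 0.5 SD difference is only about 52%. Do not substitute a rule that changes on different scales must correlate. The scales share one self-report form and recall period, and if reporting error alone correlated changes at 0.4, a lower limit above zero would be reached in about 91% of samples of 64.

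**Target 2.** Report the correlations with 95% CIs and the time point, as a check on how the scales relate, and say that they are evidence neither for nor against moderation. Confirm first which moderators are collected. The baseline survey reproduced in Appendix G has no catastrophizing, depression, oral-habit, stress or social-support items, so those correlations cannot be computed from that form.

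**Cost.** A few lines of text, slightly more analysis using outcome data already planned, and a responsiveness claim that is harder to make.
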